4.8.2. Sensitivity Analyses

The iADRS will be analyzed by mixed model with repeated measures (MMRM) and natural cubic splines (NCS) (Donohue et al., 2023) as the sensitivity analyses. For MMRM and NCS analyses, treatment effect based on data up to WK76 and based on data up to WK88 will be provided, respectively. For the latter, the ‘overall’ treatment effect averaging across Week 64, Week 76, and Week 88 will be calculated. Additional timepoints may be included for exploratory purpose.

4.8.2.1. Natural Cubic Spline (NCS) Analysis

A NCS model with 2 degrees of freedom (NCS2) (Donohue et al. 2023) will be used to estimate the difference in the change in iADRS score between the treatment arms. The NCS2 model has 3 knots over the observation time will be placed: 2 at the boundaries (minimum and maximum observation time), and 1 internal knot at the median observation time. The baseline estimates are restricted to be the same for all treatment arms. The model will be estimated using restricted maximum likelihood method (RMLE).

The iADRS score at baseline and at each of the scheduled post-baseline visits (according to SoA) will be included in model as a dependent variable. The analysis model will include the fixed effects of NCS basis expansion terms (two terms), NCS basis expansion term-by-treatment interaction (two terms), age at baseline, AChEI/memantine use at baseline (yes/no), and investigator site (pooled). Visit will be treated as a continuous variable with values equal to weeks between baseline and post-baseline exam dates, and the NCS basis function will be derived using these visits in weeks. An unstructured variance-covariance structure matrix will be used to model within-subject variance-covariance of residual errors across visits where visits are modeled as a categorical variable. If the unstructured variance-covariance structure matrix results in a lack of convergence, the following structures will be used in sequence:

- Heterogeneous Toeplitz covariance structure
- Heterogeneous autoregressive order 1 covariance structure
- Heterogeneous compound symmetry covariance structure, and
- Compound symmetry covariance structure

Mean change from baseline values, and the comparisons between change from baseline values by treatment arms will be estimated through the proper contrast set up. The Kenward-Roger approximation will be used to estimate the denominator degrees of freedom.

Percent slowing comparing to placebo group will be calculated as the least-squares (LS) estimates of differences in change from baseline between treatment groups, then divided by the LS estimates of mean change from baseline value from placebo group. A 95% CI for this percent slowing is calculated based on a Delta method (Beyene et al. 2005).

4.8.2.2. Mixed Model with Repeated Measures (MMRM) Analysis

The change from baseline score on the iADRS at each scheduled post-baseline visit (according to the SoA) during the treatment period will be the dependent variable. The analysis model includes the fixed effects of treatment, visit as a categorical variable, baseline score, baseline-by-visit

interaction, treatment-by-visit interaction, and investigator site (pooled). Baseline covariates such as age and concomitant AChEI/memantine use at baseline (yes/no) will be included in the model. An unstructured covariance matrix will be used to model the within-subject variance-covariance of residual errors across visits. If the unstructured covariance structure matrix results in a lack of convergence, the following tests will be used in sequence:

- Heterogeneous Toeplitz covariance structure
- Heterogeneous autoregressive order 1 covariance structure
- Heterogeneous compound symmetry covariance structure, and
- Compound symmetry covariance structure

The Kenward-Roger approximation will be used to estimate the denominator degrees of freedom.

The treatment group contrast in LS mean progression and its associated p-value and 95% CI will be calculated for the treatment comparison of LY3372689 versus placebo using the MMRM model specified above.

4.8.3. Supplementary Analyses

4.8.3.1. Time Progression Models for Repeated Measures (Time-PMRM) Analysis

Time-PMRM (Raket 2022) will be used to evaluate the possible slowing of the disease progression, as measured by time, with the treatment of LY3372689 in relative to placebo. The null hypothesis is that there is no slowing of the time progression of the disease in active treatment arms as compared to the placebo arm. The testing will be done by likelihood ratio test (LRT).

The iADRS score at baseline and at each of the scheduled post-baseline visits (according to the SoA) will be included in model as a dependent variable. The analysis model will include age at baseline AChEI/memantine use at baseline (yes/no), and investigator site (pooled). Weeks since randomization at each planned visit will be included as a continuous variable. The intercepts are constrained to be the same across treatment arms. An NCS with internal knots at each planned visit will be used to interpolate the disease progression between the planned visits for the placebo arm, and the trajectories of the active treatment arms will be estimated with the assumption that the mean disease progression of the active treatment arms at a given visit can be estimated by the mean disease progression of the placebo arm at another time point. The assumption of proportional time slowing will be tested. If the proportional time slowing assumption is not met, a model similar to the above but having individual time slowing parameters estimated separately at each post-baseline visit will be fitted. Model parameters will be estimated using maximum likelihood estimation (MLE).

4.8.3.2. Delta Adjustment Tipping Point Analysis

Sensitivity to departures from the MAR assumption in the MMRM analyses will be investigated using a tipping point analysis (Carpenter & Kenward 2013). This method is a sensitivity analysis in multiple imputation (MI) under the missing-not-at-random (MNAR) assumption that searches

for a tipping point that reverses the study conclusion. Departures from MAR in the active treatment arms will be assessed assuming that participants who discontinue the study have, on average, efficacy outcomes after discontinuation that are worse by some amount δ compared to other similar participants with observed data (i.e., compared to a value which would have been assumed under an MAR model). A series of analyses will be performed with increasing values of δ until the analysis conclusion of a statistically significant treatment effect no longer holds. The value of δ that overturns the primary results will represent a tipping point. An interpretation of clinical plausibility of the assumption underlying the tipping point will be provided.

Mean changes from baseline in iADRS scores will be analyzed based on data observed while the participant remains on study as well as data imputed using MI methodology for time points at which no value is observed. Imputed values in the active treatment arms will first be sampled from an MAR-based MI model and then δ -adjusted as described below.

Missing-at-random-based imputations will be generated for iADRS scores at each time point, and then a value of $\delta = \{\Delta\}$ will be added to all imputed values in the active treatment arms prior to analyzing multiply imputed data. This approach assumes that the marginal mean of imputed participant measurements is worse by δ at each time point after discontinuation compared to the marginal mean of participants with observed data at the same time point. Analyses will be conducted with values of δ starting from 0 with increments of 0.10 until the null hypothesis can no longer be rejected.

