1.3. Method of Assignment to Treatment

This is a double-blind study, with design to maintain blinding to treatment. To preserve the blinding of the study, a minimal number of Lilly personnel will see the randomization table and treatment assignments before the study is complete.

Participants who meet all criteria for enrolment will be assigned a study (patient) number at Visit 601 or Visit 1 and randomized to double-blind treatment at Visit 2. Participants will be randomized to LY3372689 or Placebo in a 1:1:1 ratio. For between-group comparability, patient randomization will be stratified by investigative site and tau burden (moderate versus high), and by prior or current use of any approved disease-modifying therapy for AD.

Assignment to treatment groups will be determined by a computer-generated random sequence using an interactive web response system (IWRS). Randomization into one stratum may be discontinued at the discretion of the sponsor. LY3372689 will be made available in blister packaging and will be given by a blinded nurse or other qualified blinded personnel, as described in the pharmacy manual. Site personnel will confirm that they have located the correct packages by entering a confirmation number found on the label into the IWRS.

For the first approximately 30 participants, the IWRS will be programmed to guarantee balance between the arms for the first interim analysis for safety; this is referred to as the burn-in period. After the burn-in period, participant randomization will then follow the dynamic allocation (minimization) method of Pocock and Simon (1975) to balance the treatment arms using investigative site as a factor. This is to ensure balanced participant assignment between treatment arms within each site at the end of the study.

2. Statistical Hypotheses

The primary efficacy analysis will be a Bayesian DPM conducted on the primary outcome iADRS. The primary efficacy analysis population will be those with moderate levels of tau pathology at baseline. A critical success factor (CSF) will be established of the following form:

- Probability (at least 25 % slowing of disease progression with LY3372689 relative to placebo) > 0.6 .

The Bayesian DPM will be utilized to calculate the posterior probability of at least 25% slowing. If the posterior probability exceeds the probability threshold for at least one LY3372689 versus placebo comparison, the trial will have been considered to have met its primary endpoint.

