4.1. General Considerations

The protocol calls for a Data Monitoring Committee (DMC) charged with making decisions regarding participant safety and study futility. This analysis plan describes analyses for the final clinical study report and all interim analyses for the DMC. Statistical analysis of this study will be the responsibility of the sponsor or its designee.

As Study MTAE is a Phase 2 study, the appropriate estimand is the efficacy of LY3372689 being assessed under the paradigm of all participants taking study drug as intended. Two intercurrent events are considered: initiation or change to standard of care disease-modifying therapy and discontinuation of the study drug prior to completing the 76-124 weeks of treatment.

The primary analysis is to use a Bayesian DPM analysis of the iADRS to compare the overall percent cognitive and functional slowing/worsening between LY3372689 versus placebo at end point (76 – 124 weeks). The same analysis set will be analyzed using Mixed-Effect Model Repeated Measure (MMRM) to serve as the sensitivity analysis. Similarly, MMRM will serve as the sensitivity analysis for each analysis of clinical progression that assessed via the DPM.

All efficacy analyses will follow the intention-to-treat (ITT) principle unless otherwise specified. An ITT analysis is an analysis of data by the groups to which participants are assigned by random allocation, irrespective of actual treatment received or participant's compliance with the protocol. even if the participant does not take the assigned treatment, does not receive the correct treatment, or otherwise does not follow the protocol. Consistent with ITT studies the estimand for Study MTAE is the Treatment Policy estimand.

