- Probability (at least 25 % slowing of disease progression on iADRS in LY3372689 high dose relative to placebo) > probability threshold 1.
- Probability (at least 25 % slowing of disease progression on iADRS LY3372689 low dose relative to placebo) > probability threshold 2.

These two thresholds will be calculated after unblinding at PODBL to establish the accurate probability thresholds that correspond to each alpha level as shown in graphical testing scheme above. As the thresholds can be sensitive to the underlying assumptions of placebo trajectory and the variance-covariance matrix, the methodological approach to find the probability thresholds is pre-specified below. The established thresholds will be documented in the CSR.

1. The NCS2 results for the iADRS (Section 4.8.2.1) from the moderate tau population will provide the underlying assumptions that are needed for this simulation. The following will be utilized: the LS mean placebo trajectory and the number of participants with data from the placebo arm at each visit; the pooled variance covariance matrix as estimated from the NCS2.
2. To create a null distribution, simulate multivariate normal data for the number of participants from the moderate tau population representing the placebo arm, assuming all participants have the same decline as the placebo arm from the NCS model and the same variability. The amount of data simulated for each treatment arm will reflect the exact number of participants at each visit from the placebo arm.
3. The posterior probability of at least 25% slowing is calculated by fitting the Bayesian DPM to each 100,000 simulated dataset. The Bayesian DPM as described in Section 4.8.1 but without covariate adjustment. The threshold is the lowest value at which at least $(\alpha/2 \times 100)\%$ of the simulated posterior probabilities are larger. Note that the probability threshold 2 will be re-calculated if it makes all the way down to tau imaging biomarker in the high dose arm.

The tests for the rest of the graph: CDR-SB, iADL, and ADAS-Cog13 will be based on the p-value of the difference of averaged LSM change across Week 64 to Week 88 between the treatment arms; tau imaging biomarker endpoint AD-signature VOI will be based on the p-value of the difference of LSM change at Week 76 between the treatment arms.

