4.15.2. Participant Characteristics

4.15.3. Listing and summary table will be provided for the Efficacy Follow-up Analysis Set. Refer to Section 4.5 for details. Analyses of Clinical and Biomarker Endpoints

The analyses of clinical and biomarker endpoints will include safety follow-up baseline (defined as the last available visit from V21 to V29 during the double-blinded period), V802, and V803. These analyses will be performed using the Efficacy Follow-up Analysis Set.

[figure not shown]
Listings and box plot will be provided for the following endpoints, if deemed appropriate.

- Clinical endpoints: iADRS, CDRSB, ADAS-Cog13, ADCS-ADL, and MMSE
- Biomarker endpoints: volumetric MRI (Hippocampal volume (mm³) and Whole brain volume atrophy (cm³)), blood-based biomarkers (plasma P-tau217, NfL, and GFAP)

Changes from both safety follow-up baseline and the original baseline at V802 and V803 will be assessed using MMRM. The analysis model includes the fixed effects of treatment, visit as a categorical variable, treatment-by-visit interaction, baseline score, and baseline score-by-visit interaction. Baseline covariates such as age, AChEI/Memantine use, pooled investigator and tau PET category will be included in the model.

5. Sample Size Determination

Approximately 330 participants will be enrolled and randomized in a 1:1:1 ratio to the 3 treatment arms (placebo and 2 active arms of LY3372689). It is expected that approximately 240 participants (i.e., 75%) will complete the double-blind Period 2a 76-week treatment period of the study (approximately 80 per treatment arm). Using a DPM model over the entire 124-week treatment period, this sample size will provide CCI

CCI. If the active LY3372689 treatment arm progression rate is not different than the placebo treatment arm rate, the probability of passing the efficacy criterion specified above (i.e., false positive) is approximately 2.4% CCI. The simulation for the power calculation and sample size determination was carried out in the statistical program R, version 3.6.3

6. Appendices

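### The only missing-not-at-random check is run on the MMRM p-value, so its tipping point does not show when the Bayesian primary result would fail

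*SAP*

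**What the plan says.** SAP 2 (Statistical Hypotheses) defines the primary analysis: "The primary efficacy analysis will be a Bayesian DPM conducted on the primary outcome iADRS". The success factor is "Probability (at least 25 % slowing of disease progression with LY3372689 relative to placebo) > 0.6", and the primary endpoint is met on this condition: "If the posterior probability exceeds the probability threshold for at least one LY3372689 versus placebo comparison". In the testing graph (SAP 4.9.2.1) the iADRS nodes also use posterior-probability cut-offs, found by simulation: "These two thresholds will be calculated after unblinding at PODBL". No p-value enters either rule.

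SAP 4.1 and 4.8.2 make the MMRM a sensitivity analysis. SAP 4.8.3.2, under Supplementary Analyses, opens with its scope: "Sensitivity to departures from the MAR assumption in the MMRM analyses will be investigated using a tipping point analysis". Delta starts at 0, rises in steps of 0.10 and is added to imputed active-arm values until the null hypothesis is no longer rejected. The section then concludes: "The value of δ that overturns the primary results will represent a tipping point".

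SAP 4.2.1 relies on missing-at-random or ignorable missingness. SAP 5 gives the expected scale: "It is expected that approximately 240 participants (i.e., 75%) will complete the double-blind Period 2a 76-week treatment period".

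**The concern.** The procedure and its label refer to different analyses. The quantity being tipped is a significance test in a sensitivity model. The quantity said to be overturned is the primary result, a posterior probability from another model with a 25% margin.

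The other planned models do not fill the gap. The natural cubic spline and time-progression models are likelihood analyses under the same missingness assumption, and the SAP version history records that completer and per-protocol analyses were removed. Neither document refits the DPM to data imputed under a missing-not-at-random assumption.

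At stake is how a positive result would be described. If the DPM passes and the MMRM does not reach significance, the search ends at delta = 0 and yields no tipping point for the claim being made. If both pass, the reported delta belongs to the other test and may make the primary result look more or less robust than it is.

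**Working it through.** **1. The plan's own figures.** 240/330 = 72.7%, whereas 330 × 0.75 = 247.5; both are offered as approximate, so 25–27% are expected not to complete 76 weeks. The stated false-positive rate of about 2.4% cannot be reproduced because its inputs are redacted. It can only be back-solved. Let m be the estimated log progression ratio (log DPR) and s its standard error. With the SAP's prior variance of 0.25 and a normal approximation, the posterior mean is m × 0.25/(0.25 + s²) and the posterior SD is s × √(0.25/(0.25 + s²)). The 0.6 rule passes when mean + 0.253 × SD < ln 0.75 = −0.288. A 2.4% rate for one arm then needs s of about 0.194.

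**2. The two rules side by side.**
- Hypothesis: MMRM tests a difference of zero; the DPM asks whether the ratio is below 0.75.
- Mean: MMRM has free visit-wise effects; the DPM has one proportional ratio across visits (4.8.1).
- Covariance: MMRM is unstructured; the DPM has a random intercept with independent errors.
- Window: 4.8.2 gives the MMRM two (to Week 76; to Week 88, averaging Weeks 64, 76 and 88), and 4.8.3.2 does not say which applies. The DPM uses all visits that are not sparse (4.1).

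Even on the same log-ratio scale, the 0.6 rule is not a 1.96 rule:

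| s | Slowing needed, 0.6 rule | Slowing needed, z = 1.96 |
|---|---|---|
| 0.12 | 28.5% | 21.0% |
| 0.20 | 32.2% | 32.4% |
| 0.25 | 35.0% | 38.7% |

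**3. Tipping points under assumed inputs.** Not in the documents: 70 or 110 per arm; placebo decline D of 10 or 14 points at Week 76; slope SD 9 or 13; intercept SD 11; residual SD 5; 26% dropout by Week 76; half of those remaining seen at Week 88. A shift δ worsens the active mean at Week 76 by 0.26 × δ. So the MMRM tips at δ = (difference − 1.96 × SE)/0.26, and the DPM tips approximately at δ = (critical ratio − true ratio) × D/0.26.

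- *110 per arm, D = 14, slope SD 9, 30% slowing.* MMRM: difference 4.2, SE 1.663, δ = (4.2 − 3.26)/0.26 = 3.6. DPM: posterior SD 0.080; (−0.288 − 0.253 × 0.080)/(1 − 0.080²/0.25) = −0.316, a critical ratio of 0.729; δ = (0.729 − 0.70) × 14/0.26 = 1.6. The MMRM overstates robustness.
- *70 per arm, D = 14, slope SD 13, 40% slowing.* MMRM: (5.6 − 1.96 × 2.678)/0.26 = 1.4. DPM: 6.3. The MMRM understates it.
- *70 per arm, D = 10, slope SD 9, 40% slowing.* MMRM at Week 76: z = 4.0/2.084 = 1.92, so no tipping point exists. DPM: posterior ratio 0.628, SD 0.148, probability 0.885; it tips at about 4.1.

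Over 32 combinations (slowing 30, 35, 40 or 50%), the DPM passed while the Week 76 MMRM failed at δ = 0 in 12; in 11 of these the Week 64–88 average failed too. These counts describe a grid and are not probabilities.

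**4. Size of the missing-data question.** Assume linear decline, uniform leaving times and no further benefit after leaving. The share of the effect kept at Week 76 is then 1 − (1 − completion) × (share of non-completers leaving the study) × 0.5.

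| Share leaving | Kept (72.7% / 75% completing) | 25% slowing becomes |
|---|---|---|
| All | 0.864 / 0.875 | 21.6 / 21.9% |
| Three quarters | 0.898 / 0.906 | 22.4 / 22.7% |
| Half | 0.932 / 0.938 | 23.3 / 23.4% |

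The loss is about 6–14% of the effect. Weighting the scheduled visits to Week 76 by squared decline, closer to how a single ratio is fitted, gives 0.889–0.898 when all leave, a loss of 10–11%.

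**The case against.** The section's opening sentence confines the analysis to the MMRM, it is listed as supplementary, and a tipping point on a declared sensitivity model is a legitimate check on the same endpoint. The MMRM result is reported in any case, so a reader would see disagreement with the DPM. In the grid above, the Week 76 MMRM delta was the larger of the two in only 4 of the 19 combinations where both analyses passed, so it would often be the more cautious figure. All of this stands, and it makes the MMRM analysis worth keeping. It does not make the MMRM delta a tipping point for the primary result.

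Two stronger readings are tempting.

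- *That the primary estimate is overstated by 12–14%.* This needs every non-completer to leave the study, whereas Protocol 7.1 lets participants stop drug and continue assessments, and no split is given. It also needs a treatment-policy reading. Protocol 9.1 supports one, and SAP 4.1 says "Consistent with ITT studies the estimand for Study MTAE is the Treatment Policy estimand", but SAP 1.1 and another part of 4.1 describe effects while on treatment or with drug taken as intended. Under that wording, carrying the arm's ratio forward is not a bias.
- *That the DPM and MMRM would disagree in about a third of successful trials.* A simulation with 85 per arm, a 10-point decline, slope SD 8 or 12, residual SD 5 and 73% completing gave 28–36% of DPM-passing trials at a true ratio of 0.75, and 15–22% at 0.55. All those inputs are assumed, and the cut-offs were calibrated to one-sided 2.5% (0.637 and 0.904) instead of set at 0.6. The rates largely reflect a power difference between a one-parameter model and a visit contrast.

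**Conclusion.** The point holds on the text. The delta defined in SAP 4.8.3.2 marks where the MMRM loses significance. It cannot show where the primary criterion fails, and no planned analysis stresses the DPM's own missing-at-random handling. This is true under either reading of the estimand.

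The documents do not allow a rate of disagreement or a bias to be stated. The worked examples show only that the two tipping points can differ in either direction and that the MMRM one may not exist; they rest on assumed decline, variance, sample size and dropout. The 6–14% range is likewise illustrative and applies only under treatment policy.

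The same section has a sign problem. By the scoring in SAP 4.2.2, lower iADRS is worse, so adding a rising positive delta would, taken literally, improve the active arms and never tip. The stated intent is clearly the opposite.

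**What to change.** In SAP 4.8.3.2:

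1. Also fit the primary DPM (4.8.1) to the delta-adjusted multiply imputed data sets, pool the posterior draws, and report for each dose the delta at which the probability of a ratio below 0.75 falls to 0.6.
2. Report the testing-graph thresholds as a secondary reference. They are calibrated to the placebo arm's observed visit counts (4.9.2.1), so either say that they lose their exact alpha meaning on imputed data or recalibrate them.
3. State that delta is subtracted from imputed active-arm iADRS values.
4. Keep the MMRM tipping point, state its time window, and say that it overturns the MMRM result, not the primary results.
5. Optionally, run one reference-based imputation through the same DPM, with withdrawn active-arm participants following placebo increments, as a treatment-policy sensitivity analysis.

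The cost is SAP wording and repeated DPM fits. No new data are needed and the primary decision rule is unchanged.

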With the 76-week common close design and given the backloaded enrollment progress in reality, the observations collected during the common close period such as Week 88 and onward could be too sparse for a proper data interpretation, especially for repeated measures models such as MMRM and natural cubic spline (NCS) models. The 'sparse' at a given timepoint/visit is defined as less than 10 datapoints per study arm. Unless otherwise noted, the full analyses set in terms of analysis visits for all longitudinal analysis models is data up to the timepoint where the post Week 76 visit that meets the requirement of > 10 datapoints per study arm at a given timepoint/visit in moderate tau population and the same will apply to full study population. Observations collected beyond *this* post Week 76 visit may be included for exploratory purpose.

For clinical efficacy endpoints (cognitive and functional scales) and biomarker endpoints assessed by repeated measures and disease progression models, observations collected at nonscheduled visits will not be included in the analyses unless the nonscheduled visit coincided with a protocol scheduled visit (Anderson and Millen, 2013). For analyses using last observation carried forward (LOCF), the last non-missing postbaseline observation (scheduled or unscheduled) will be used to calculate change from baseline.

Unless otherwise noted, baseline is defined as the last measurement prior to the initiation of the first dose, and endpoint is the last non-missing postbaseline measurement within the time period for the given analysis. Baseline definitions for safety analyses is described in Table 4.1. When

change from baseline is assessed, subjects will only contribute to the analysis if both a baseline and a postbaseline measurement are available.

Unless otherwise noted, all pairwise tests of treatment effects will be conducted at a 2-sided alpha level of 0.05 (or a 1-sided 0.025 alpha level if appropriate); 2-sided confidence intervals (CIs) will be displayed with a 95% confidence level. All tests of interactions between treatment and other factors will be conducted at an alpha level of 0.05.

Unless otherwise noted, no formal statistical hypothesis testing will be made for the safety interim analyses. Any reported p-values that may be reported as part of standardized output are merely for information purposes only.

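### SAP 4.8.3.2 assumes a penalty for dropouts only, but its rule shifts every imputed active-arm value; on the Week 64/76/88 average, with delta read as a worsening, the tipping point would be about 11–27% too small

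*SAP*

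**What the plan says.** SAP 4.8.3.2 gives its purpose as follows: "Sensitivity to departures from the MAR assumption in the MMRM analyses will be investigated using a tipping point analysis". The assumption is limited to dropouts, namely that "participants who discontinue the study have, on average, efficacy outcomes after discontinuation that are worse by some amount" delta. The sentence after the delta rule again describes the shift as applying after discontinuation.

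The operating instructions are not limited in this way. The analysis uses observed data plus "data imputed using MI methodology for time points at which no value is observed", and delta "will be added to all imputed values in the active treatment arms prior to analyzing multiply imputed data". No sentence separates dropout from a missed visit or from a visit that fell after the common close.

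Two MMRM results are planned in SAP 4.8.2: "For MMRM and NCS analyses, treatment effect based on data up to WK76 and based on data up to WK88 will be provided, respectively". In the second, an overall "treatment effect averaging across Week 64, Week 76, and Week 88 will be calculated". Section 4.8.3.2 does not say which of the two it tests. On the data expected after Week 76, SAP 4.1 warns that, with backloaded enrolment, "the observations collected during the common close period such as Week 88 and onward could be too sparse for a proper data interpretation".

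**The concern.** A programmer following the rule as written would treat planned administrative closure and withdrawal as the same event, and in the active arms only. Someone who completed the trial as designed, but was only a few weeks past Week 76 at the close, would have Week 88 imputed and then marked down as if they had dropped out. An isolated missed visit would be treated in the same way.

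The delta at which significance is lost would then depend partly on enrolment timing. The SAP promises a judgement on whether the tipping delta is clinically plausible. That judgement would be made on a number mixing two unrelated causes of missing data, and a result that withstands dropout could look fragile.

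**Working it through.** **The plan's own figure.** The only missing-data figure in the documents is in SAP section 5: about 240 of 330 completing Week 76, labelled 75%. In fact 240/330 = 72.7%, and 330 × 0.75 = 247.5. The gap is small for a figure given as approximate. I use dropout d = 0.25 and check 0.273.

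**Who loses Week 88 to the close.** Protocol 4.1.2 gives everyone who stays at least 76 weeks of assessments, so nobody loses Week 76. In Protocol 1.3.3 the visits after Week 76 are a Week 82 televisit and then Week 88. Protocol 4.1.3 places the end-of-study visit at the next scheduled visit, so a participant at Week 76–82 at the close finishes without a Week 88 assessment. Footnote f of 1.3.3 instead places that visit at the time of the close, with cognitive testing only in a scheduled window or more than 10 weeks after the last test. On that reading the affected span is about 10 weeks. So roughly the last 6 to 10 weeks of enrolment lose Week 88.

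**Share affected (assumption).** Let a be the share of remaining participants lacking Week 88 because of the close. The documents do not give it. Taking the enrolment span as 124 − 76 = 48 weeks:

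- Uniform enrolment: 6/48 = 12.5%; 10/48 = 20.8%.
- Linearly rising (backloaded) enrolment: 1 − (42/48)² = 23.4%; 1 − (38/48)² = 37.3%.

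**Effect on the tipping point.** The active-arm mean falls by delta times the share of values shifted, averaged over Weeks 64, 76 and 88. If discontinuers are missing at all three visits:

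- Share shifted, discontinuers only: d.
- Share shifted, as written: d + (1 − d)a/3.
- Ratio of tipping points, written to dropout-only: d / [d + (1 − d)a/3].

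With d = 0.25:

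| a | share shifted as written | ratio | factor |
|---|---|---|---|
| 0.125 | 0.281 | 0.89 | 1.12 |
| 0.208 | 0.302 | 0.83 | 1.21 |
| 0.234 | 0.309 | 0.81 | 1.23 |
| 0.373 | 0.343 | 0.73 | 1.37 |

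With d = 0.273 the ratio is 0.90 at a = 0.125 and 0.75 at a = 0.375. For the Week 76 MMRM, a = 0 and the ratio is 1.00. If some discontinuers leave after Week 64, the dropout-only share is a little smaller and the understatement a little larger. Intermittent gaps are not in the formula; they would be shifted in either MMRM.

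**Simulation check.** The formula holds the standard error fixed. A simulation with an assumed trajectory and SD, 110 per arm, 25% dropout, multiple imputation by arm and the SAP's 0.10 grid gave median ratios of 0.90, 0.81, 0.73 and 0.70 for a = 0.125, 0.25, 0.375 and 0.50. The formula gives 0.89, 0.80, 0.73 and 0.67. At a = 0 the simulated ratio was 1.00.

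**Direction of delta.** SAP 4.2.2 defines iADRS as 85 minus ADAS-Cog13 plus ADCS-iADL, so higher is better. Adding a positive delta therefore improves the imputed active-arm scores. With that literal sign, no tipping point was reached in any of 10 simulated trials up to delta = 80, under either rule.

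**The case against.** The strongest defence is that the delta sentence sits between two statements tied to discontinuation. In context, the imputed values it refers to could be read as post-discontinuation values only. That is a fair reading of intent, and it is why this is an internal contradiction and not a deliberate penalty on completers. It does not remove the problem, because the instruction on what to impute covers every unobserved time point.

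A second defence is that the Week 76 MMRM may be the one intended. If so, the common-close part of the problem disappears. The section does not say.

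A reader might also infer from the sparsity warning that most missing Week 88 values belong to completers, or that the tipping delta is understated by as much as 1.76-fold. The documents do not support either. The warning says only that data could be sparse. The larger factor needs about 15 of 110 observed per arm at Week 88, so with 80 completing Week 76, 65 of 80 (81%) would have to be cut off by the close. The visit schedule points to 12.5–37% under the enrolment assumption. On that range, the non-dropout share of imputed Week 88 values, (1 − d)a/[d + (1 − d)a], is 27–53%.

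The analysis covers the moderate-tau population, which is smaller than 110 per arm. The ratio depends only on proportions, so it stands if those are similar.

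**Conclusion.** The contradiction in SAP 4.8.3.2 is real. If the Week 64/76/88-average MMRM is tested and delta is read as a worsening, the tipping delta comes out about 11–27% too small. That size rests on 25% dropout, a 48-week enrolment span and 12.5–37% of remaining participants lacking Week 88; only the dropout figure comes from the plan. The common close has no effect on the Week 76 MMRM.

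A reader might infer that the trial's main conclusion is at risk. It is not. The primary analysis is the Bayesian DPM, the MMRM of iADRS is a sensitivity analysis, and the tipping point is supplementary to that and informative only if the MMRM is significant. With delta as a worsening, the error makes a positive result look more fragile and cannot create a false claim. The impact is modest, but the promised plausibility judgement needs the right delta.

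**What to change.** Amend SAP 4.8.3.2 in four respects:

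- Name the MMRM time point being tested (Week 76, the Week 64/76/88 average, or both).
- Apply delta only to imputed active-arm values at scheduled visits after the participant's study discontinuation date. This includes Week 88 for those who left earlier, as the calculation above assumes.
- Impute intermittent gaps, and visits not reached because of the common close, under MAR without delta.
- State that delta is subtracted from iADRS, since a higher score is better.

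The cost is a short text change and one flag in the imputation program. Disposition information is already collected (SAP 4.4), so no new data are needed. If the double-blind data have already been unblinded, record the clarification in the CSR and show the result under both rules.
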